8. STATISTICAL METHODS

8.1. General Principles of Data Analyses

The primary analysis for this study will be performed and summarized after all randomized subjects have had an opportunity to complete their 9-month follow-up visit.

The primary analyses of the safety endpoints will be based on the Safety population. The primary analyses of the efficacy endpoints will be based on the ITT population. Additional sensitivity analyses for the primary and secondary efficacy endpoints will be performed to further assess the effects of the treatment (Section 8.4.4).

The statistical analyses will be reported using summary tables, figures and listings. Continuous variables will be summarized with means, standard deviations, medians, minimums, maximums, 25th percentiles, 75th percentiles, and number of non-missing observations for each treatment group.

Categorical variables will be summarized by counts and by the percentage of subjects in corresponding categories.

All inferential statistical analyses will be performed with a two-sided confidence level of 95% or a two-sided significance level of 0.05 unless otherwise noted.

All analyses and tabulations will be performed using SAS[®] Version 9.4 or higher on a Server platform.

8.2. Subject Enrollment and Disposition

The reasons for subject enrolled but not randomized (including screen failures) will be summarized by the specific inclusion/exclusion not met for screen failures and any other reasons provided. Subject disposition will be summarized for all randomized subjects. The summary including the number and percentage (based on total number of subjects randomized) of subjects in each of the following categories will be prepared:

- Available at each of the protocol-specified visits based on the ITT population
- Completing 9-month blinded assessment based on the ITT population
- Early Termination based on the ITT population

• Safety population, ITT, mITT, and PP populations.

Major protocol deviations for subjects not in the Per-Protocol Populations will be listed.

8.3. Demographics and Baseline Characteristics

The following outcomes will be summarized by the standard methods for continuous and categorical variables described in Section 8.1.

The demographics include the following parameters:

- Age at informed consent
- Sex
- Race
- Ethnicity.

The baseline characteristics include the following:

- Use of gabapentin and/or pregabalin
- Baseline average 24-hour pain score obtained from the Daily Pain and Sleep Interference Diary
- Baseline average sleep interference score obtained from the Daily Pain and Sleep Interference Diary
- Vital signs: blood pressure, weight, BMI, heart rate, respiration rate, temperature
- Physical examination: head, eyes, ears, nose, and throat (HEENT), heart, lungs, abdomen, extremities, lymph nodes, musculoskeletal, neurological, and gastrointestinal systems. Any abnormalities are categorized as clinically significant (CS) or not clinically significant (NCS).
- Diabetes type
- Medical history categorized by Medical Dictionary for Regulatory Affairs (MedDRA) System Organ Class (SOC) and preferred term (version 21.0 or later)
- Symptoms of BPNS: total score for right and left leg separately and combined.
- Cancer screening findings: Positive and Negative

- Viral screening findings: Positive and Negative
- 12-lead ECG: Normal, Abnormal NCS, Abnormal CS
- Urine pregnancy test: Positive, Negative, and Not Applicable.

These parameters will be summarized by treatment group for the ITT and included in data listings. Other collected baseline characteristics will be listed only. The demographic and selected baseline characteristics (diabetes type and specific medical history items of interest) will also be summarized for each level of the stratification variable. Particular medical histories of interest, based upon MedDRA SOC and preferred terms, will be determined by the CDRC in a blinded fashion prior to analyses.

8.4. Efficacy Endpoints Analyses

8.4.1. Primary and Secondary Efficacy Endpoints

Subjects will be asked to assess the level of pain they feel by selecting a score from 0 (No Pain) to 10 (Worst Possible Pain) in the Daily Pain and Sleep Interference Diary for 7 days at screening (the baseline for the pain score), 3-month, 6-month, and 9-month visits. The Daily Pain and Sleep Interference Diary must be completed within the 14 days prior to each specified visit. The average of the available pain scores from the Daily Pain and Sleep Interference Diary will be calculated for each subject at each visit and will be rounded to the first decimal point.

The primary efficacy endpoints are the change in average 24-hour pain score as determined by the Daily Pain and Sleep Interference Diary between baseline and the 3-month follow-up and outcome of a pain score change of \leq -50% at 3 months. The change and the percent change in pain will be calculated for each subject as follows:

Change = 3-month Pain Score – Baseline Pain Score

% Change = Change \div Baseline Pain Score \times 100%.

Since higher scores indicate worse pain, a negative value of change means an improvement, and a positive value of change means deterioration. Subjects with a percent change of \leq -50% (i.e., reduction of at least 50%) will be classified as a responder at 3 months. The means of the change in the average 24-hour pain score at 3 months and the percentage of subjects with a change in the average 24-hour pain score of \leq -50% will be compared between the treatment groups (VM202 and placebo) at 3 months.

The key secondary efficacy endpoints are the change in the average 24-hour pain score from baseline to the 6-month follow-up, and the outcome of reduction in average 24-hour pain score of at least 50% at 6 months. The means of the change in the average 24-hour pain score at 6 months and the percentage of subjects with a change in the average

24-hour pain score of \leq -50% will be compared between the treatment groups (VM202 and placebo) at 6 months.

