4. STUDY ENDPOINTS

4.1. Primary Efficacy Endpoints

There are two primary efficacy endpoints that will be evaluated in sequential order. The primary efficacy endpoints are as follows:

- 1. The change in the average 24-hour pain score from baseline to the 3-month follow-up [Day 90] obtained from the Daily Pain and Sleep Interference Diary.
- 2. The outcome of at least a 50% reduction (i.e., ≥ 50%) in the average 24-hour pain score from baseline to the 3-month follow-up obtained from the Daily Pain and Sleep Interference Diary.

The statistical hypotheses for the first primary efficacy endpoint are:

H₀: $\mu_t = \mu_p$ versus H_a: $\mu_t \neq \mu_p$, (I)

where μ_t and μ_p are the mean pain change from baseline to the 3-month follow-up for the VM202 and Placebo groups, respectively. A negative mean value indicates a reduction in the pain score, and a positive mean value indicates an increase in the pain score.

If the null hypothesis for the first primary efficacy endpoint above is rejected, then the formal statistical test will be performed for the second primary efficacy endpoint. The statistical hypotheses for the second primary efficacy endpoint are:

H₀: $p_t = p_p$ versus H_a: $p_t \neq p_p$, (II)

where p_t and p_p are the percentage of subjects with a change in the average 24-hour pain score from the Daily Pain and Sleep Interference Diary from baseline to the 3-month follow-up of a \leq -50% (i.e., a reduction of \geq 50%) for the VM202 and Placebo groups, respectively.

Since the formal statistical test for the second primary efficacy endpoint will not be performed if the null hypothesis of the first primary endpoint is not rejected, the significance level for both sets of the statistical hypotheses is not adjusted and kept at a two-sided 0.05.

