7.7. Missing Average 24-hour Pain Scores at 3, 6, or 9 Months

The Daily Pain and Sleep Interference Diary is to be completed within 14 days of the 3-, 6- and 9-month visits. The average 24-hour pain score for a visit will be considered as missing if fewer than 5 of 7 days of Daily Pain and Sleep Interference Diary entries are provided. Sensitivity analyses for the mean change in the average 24-hour pain score will include the following imputation approaches for missing values at 3-months, 6-months, or 9-months. It is important to note that over-stratification may result when the total list of pre-specified factors are considered. Under this scenario, the least represented factor will be removed and the imputation will be re-run. This process will be followed until the imputed dataset is complete.

- Multiple imputation: Each missing pain score will be imputed ten times to generate ten imputed complete data sets based on the Markov Chain Monte Carlo (MCMC) method with baseline pain score, 3-month, 6-month, 9 month pain score, and categorical covariates of baseline use of gabapentin and/or pregabalin, baseline HbA1c, gender, and age. The imputed score will be rounded to the first decimal point. The results of the ten tests from the continuous Repeated Measures Model (Section 8.4.2) using these data will be combined.
- Mean of the other group $(MOTH)^3$ as follows:
 - 1. For a subject with a missing 3-month, 6-month, or 9-month average 24-hour pain score, identify the subject's following baseline characteristics:
 - Study treatment group
 - Baseline use of gabapentin and/or pregabalin.

³ Unnebrink K and Windeler J, "Intention-to-treat methods for dealing with missing values in clinical trials of progressive deteriorating diseases," Statistics in Medicine, 2001;20: 3931-3946.

- Baseline average 24-hour pain score (< median or \geq median)
- HbA1c (< median or \geq median)
- Gender (male or female)
- Age (<65 years and \geq 65 years).
- 2. The missing 3-month, 6-month, or 9-month average 24-hour pain score will be imputed by using the mean average 24-hour pain score obtained at the same time point of those subjects in the other treatment group who match the subject's baseline characteristics. For example, for the missing pain scores of the VM202 subjects, the mean pain scores of the placebo subjects within the same covariate groups will be used to impute the missing pain scores.

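### Rounding diary means to one decimal before the 50% cut scores some exact 50% reductions as failures and, when diary lengths differ, some smaller reductions as responses

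*SAP*

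**What the plan says.** SAP 8.4.1 collects daily scores "for 7 days at screening (the baseline for the pain score), 3-month, 6-month, and 9-month visits". The average of the available scores, taken for every subject and visit, "will be rounded to the first decimal point". The next paragraph gives the derivation, "Change = 3-month Pain Score – Baseline Pain Score", divides by the baseline score to get percent change, and classes a percent change of -50% or lower as a response. Exactly 50% therefore counts. Nothing says that unrounded means are kept for the cut.

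The endpoint itself carries no rounding. SAP 4.1 gives it as "The outcome of at least a 50% reduction", and protocol 6.3.1 likewise applies no rounding.

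Diary length can vary. Under SAP 7.7 a visit's mean is "considered as missing if fewer than 5 of 7 days of Daily Pain and Sleep Interference Diary entries are provided", so 5, 6 or 7 days are all valid and the count may differ between baseline and follow-up. SAP 7.7 also rounds imputed scores to one decimal before they enter the sensitivity analyses.

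**The concern.** Read in order, SAP 8.4.1 makes rounding part of the derivation and not of the display. A threshold applied to rounded inputs is not the same as the threshold stated in the endpoint, and the difference falls on subjects at or just short of the cut.

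The same scores feed the 6-month responder endpoint and the exploratory cuts at 20% to 70% in SAP 4.3. The second primary endpoint is also a gate: under SAP 7.4 and 8.4.3 neither key secondary endpoint is tested unless both primary endpoints succeed. The rule is the same in both arms, so the concern is accuracy at the margin, not bias toward either arm. A further practical risk is that someone recomputing responders from the raw diaries could obtain a different count from a program that follows 8.4.1.

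**Working it through.** **The plan's own figures (SAP 5).** Inputs: responder rates 35% and 18%, two-sided alpha 0.05, power 90%, allocation 2:1. The pooled rate is (0.18 + 2 × 0.35)/3 = 0.2933. Placebo n = [1.960 × √(1.5 × 0.2933 × 0.7067) + 1.2816 × √(0.18 × 0.82 + 0.35 × 0.65/2)]² / 0.17² = (1.093 + 0.655)² / 0.0289 ≈ 105.7, so 106 placebo and 212 VM202, as stated. The pain-change endpoint needs 286 + 143 = 429 (t-test power 90.1%), and 429/0.9 = 476.7, rounded up to 477. All reproduce. At 286/143 the responder test has 96.7% power.

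**Two worked cases.**
- Equal days: baseline 36/7 = 5.143, rounded 5.1; follow-up 18/7 = 2.571, rounded 2.6. True reduction 50.00%; scored 1 − 2.6/5.1 = 49.02%, a non-responder.
- Unequal days: baseline 21/5 = 4.2; follow-up 15/7 = 2.143, rounded 2.1. True reduction 48.98%; scored 1 − 2.1/4.2 = 50.0%, a responder.

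**Full enumeration.** Every pair of whole-number diary sums was checked in exact arithmetic, with baseline mean at least 4 (SAP 7.1) and 5, 6 or 7 days at each visit: 20,313 pairs. No mean falls on a rounding tie, so the tie convention does not matter.

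| Days at baseline / follow-up | Exact-50% pairs | Of these, scored non-responder | Below-50% pairs scored responder |
|---|---|---|---|
| 7 / 7 | 22 | 6 | 0 |
| 6 / 6 | 19 | 6 | 0 |
| 5 / 5 | 16 | 0 | 0 |
| 5 / 6 | 7 | 0 | 6 |
| 5 / 7 | 4 | 0 | 9 |
| 6 / 5 | 4 | 0 | 3 |
| 6 / 7 | 4 | 0 | 6 |
| 7 / 5 | 4 | 0 | 3 |
| 7 / 6 | 7 | 0 | 6 |
| Total | 87 | 12 | 33 |

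No reduction greater than 50% is ever lost. The lowest true reduction scored as a response is 48.57% (25/6 then 15/7). At each of the 20, 30, 40, 60 and 70% cuts the same enumeration finds misclassified pairs in both directions.

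**How many subjects.** The documents contain no day-level diary data, so this part is simulation. Assumed: baseline mean 6.3, SD 1.3; SD of change 2.5; mean change −2.2 (VM202) and −0.8 (placebo), which give response rates near 35% and 18%; daily SD 0.9; incomplete diaries split 60% six-day and 40% five-day. Expected counts among 318 + 159:

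| Share of diaries complete | Responders lost | Responders gained | Total misclassified |
|---|---|---|---|
| 100% | 0.92 + 0.31 = 1.23 | 0 | 1.23 |
| 90% | 0.75 + 0.25 = 1.00 | 0.20 + 0.08 = 0.28 | 1.28 |
| 70% | 0.47 + 0.18 = 0.65 | 0.53 + 0.18 = 0.71 | 1.36 |
| 50% | 0.34 + 0.11 = 0.45 | 0.72 + 0.24 = 0.96 | 1.41 |

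Varying the daily SD from 0.5 to 1.4 barely changes these. With the Phase II ITT means and SDs from SAP Table 2 (assumed baseline mean 6.6, daily SD 1), up to 0.30% are lost with complete diaries (0.0030 × 477 = 1.4), and about 0.17% go each way with mixed lengths (0.0034 × 477 = 1.6). Lowering the planned rates by the complete-diary loss, 0.3 points for VM202 and 0.2 for placebo, moves power at 286/143 from 96.7% to 96.6%.

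**Could one subject matter?** With 25 of 143 placebo responders, 75 of 286 on VM202 gives p = 0.044 and 74 of 286 gives p = 0.052. This is the uncorrected chi-square test used for sizing, not the planned mixed model, and serves only as illustration.

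**The case against.** The rounded score can be defended as an operational definition: it is fixed in advance, deterministic and identical in both arms. On that view nobody is misclassified; the endpoint is simply measured to one decimal. It is also an inference, though the natural one, that percent change uses the rounded values. The effect is tiny, only exact ties are lost, the gains need unequal diary lengths, and with mixed lengths the two directions partly cancel. Any binary endpoint can turn on one subject when the result is borderline. Applying the rate to all 477 also overstates the count, since the plan expects 429 with 3-month data.

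Most of this stands as a limit on importance. On 429 subjects the 1.2 to 1.4 above becomes about 1.1 to 1.3. The defence of the definition is weaker: both documents state the endpoint as a reduction of 50% or more, and a subject whose recorded pain exactly halves meets it in plain terms. With complete diaries, the intended case, every discrepancy counts such a subject as a failure.

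Two objections to the remedy are useful. Changing 8.4.1 alone would leave unrounded observed scores beside rounded imputed ones from 7.7. And comparing unrounded means in floating point mishandles some exact ties at other cuts (8 pairs at 20%, 3 at 30%, 6 at 40%), though none at 50%. Both are dealt with in the fix.

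**Conclusion.** The point holds, and it is minor. The losses and the gains both follow from the SAP's own rule; the pair counts are exact and need no assumption beyond whole-number daily scores. The number of subjects affected, about 1 to 2 of 477 and nearer 1 at the planned response rates, depends on assumed baseline and day-to-day variation and on how many diaries are incomplete. Power and sample size are effectively unchanged. The consequence is confined to a borderline responder result, where one subject could decide whether the secondary endpoints are tested. The change is worth making because rounding at this step brings no analytic benefit.

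**What to change.** In SAP 8.4.1, state that change, percent change and responder status are derived from unrounded diary means, and that rounding applies only to displayed values. An exact alternative uses sums and day counts: with sums S_B and S_F over d_B and d_F completed days, a subject is a responder if 2 × S_F × d_B ≤ S_B × d_F. For a general cut of c%, the condition is 100 × S_F × d_B ≤ (100 − c) × S_B × d_F, which also avoids floating-point ties at the exploratory cuts. In SAP 7.7, drop the rounding of imputed scores so that the sensitivity analyses treat observed and imputed values alike.

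The cost is one sentence in 8.4.1, matching edits in 7.7 and a small program change. No new data, sample-size change or change to trial conduct is needed. It should be made before unblinding, so that the choice cannot appear to depend on the result.

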The model will include treatment, visit, treatment-by-visit interaction, baseline use of gabapentin and/or pregabalin, and baseline average 24-hour pain scores as covariate with an unstructured variance-covariance matrix. The point estimates for the least-squares mean of the treatment difference (VM202 – Placebo) at 3 months and the corresponding 95% confidence interval and p-value will be summarized.

The SAS code to be used to conduct the analysis is presented below:

PROC GLIMMIX DATA=work method=quad(Qpoint=); class usubjid trtp avisitn basemed;
MODEL critvar(event='Y') = trtp base avisitn basemed trtp*avisitn / DIST=binary
LINK=LOGIT SOLUTION;
random INTERCEPT / SUBJECT=usubjid type=un;
lsmeans trtp *avisitn / diff cl;
RUN;

Where USUBJID: subject ID
TRTP: treatment
AVISITN: variable representing visits (Primary model will include the 3, 6, and 9 month visits)
CHG: change in average pain score from baseline
BASE: baseline average pain score
BASEMED: a Y/N variable indicating if the subject took gabapentin/pregabalin at baseline.
CRITVAR: a Y/N variable indicating if the subject had at least a 50% reduction in baseline pain score from baseline at that visit
Qpoint: Number of quadrature nodes to clarify the dimensionality

Other variance-covariance structures selected from among compound symmetry, Toeplitz, and autoregressive (1) options will be substituted based on the lowest AIC if convergence problems arise.

8.4.3. Primary Analysis of the Secondary Efficacy Endpoints

Analyses for the primary efficacy endpoints described in Section 8.4.2 will automatically produce the analysis results for the key secondary efficacy endpoints. The point estimate for the least-squares mean of the treatment difference (VM202 – Placebo) at 6 months and the corresponding 95% confidence interval and p-value will be summarized. To control the overall significance level, statistical inferences regarding the treatment effect on secondary efficacy endpoints will be made only if the treatment effect on both primary efficacy endpoints are statistically significant in their respective primary analysis.

8.4.4. Sensitivity Analysis of the Primary and Secondary Efficacy Endpoints

To further evaluate the robustness of the primary and secondary efficacy outcomes, the Repeated Measures Model analyses described in Section 8.4.2 will be performed on the imputed data sets described in Section 7.7.1.

Additionally, two sets of the Repeated Measures Model analyses will be performed without missing value imputation. For the first set, analysis will be conducted in the ITT, mITT, and PP populations using all available average 24-hour pain score data (i.e., observed cases). For the second set conducted in the ITT and mITT populations, any individual pain scores influenced by the protocol-prohibited concomitant medications, as described in Section 6.4, will also be excluded.

The point estimates for the least-squares mean of the treatment difference (VM202 – Placebo) at 3 and 6 months, and the corresponding 95% confidence intervals and p-values, will be summarized.

8.4.5. Subgroup Analysis of Primary and Secondary Efficacy Endpoints

The subgroups are described in Sections 4.6 and 6.5. For each subgroup of the ITT population, the change in average 24-hour pain score will be summarized by treatment group and visit using descriptive statistics including mean, median, standard deviation, minimum, and maximum. The count and percentage of subjects with a change in the average 24-hour pain score will also be summarized by treatment group and visit for each subgroup of the ITT population. Both types of descriptive summaries are also provided for the subgroups of baseline use of gabapentin and/or pregabalin, study center, and protocol version. Subjects will be assigned to a protocol version based on their randomization date and the date of IRB approval at their site.

Except for the subgroups of baseline use of gabapentin and/or pregabalin, study center, and protocol version, the Repeated Measures Model analyses described in Section 8.4.2 will be performed within each subgroup.

Additionally, the possible treatment-by-subgroup interaction will be tested for each subgroup variable as follows:

- A subgroup variable will be included in the primary analysis models described in Section 8.4.2 along with its interaction with the treatment effect. If the p-value of the interaction term is ≥ 0.05, the treatment-by-subgroup interaction is not significant.
- If the interaction effect is statistically significant (i.e., p-value < 0.05), then the Gail and Simon⁵ test will be used to test for the qualitative interaction at a significance level of 0.05 and provided as an aid for interpretation.

⁵ Gail MH and Simon R. Testing for qualitative interactions between treatment effects and patient subsets. Biometrics, 1985;41: 361-372.

The Repeated Measures Model analyses described in Section 8.4.2 already account for the subgroups of baseline use of gabapentin and/or pregabalin (i.e., Yes and No groups). For evaluating the interaction between treatment and baseline use of gabapentin and/or pregabalin, the interaction effect will be added to the primary analysis models. If the interaction effect is significant, then the Gail and Simon test will be used to test for the qualitative interaction at a significance level of 0.05.

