4.6. Planned Covariates

As defined in the primary analysis of the primary and secondary efficacy endpoints, the baseline pain and the randomization stratification factor (i.e., baseline use of gabapentin and/or pregabalin) with be introduced as covariates within the models.

As a separate secondary examination of the primary and secondary efficacy endpoints, three additional covariates will be introduced into the model to derive the covariate-adjusted estimates. (ref. Section 8.4.6 for additional details):

- Baseline HbA1c (\leq and \geq median)
- Gender (male and female)
- Age (<65 years and \geq 65 years).

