5. SAMPLE SIZE CALCULATION

Table 2 provides the summary statistics for the corresponding efficacy endpoints based on change in the average pain score for the low dose and placebo groups from the intent-to-treat population and efficacy groups in the Phase II study (Protocol VMDN-002, injections at Day 0 and Day 14 only).

	ľ	T	EFFICACY				
	VM202	PLACEBO	VM202	Placebo			
		Mean ((SD)				
Month 3	-2.89 (2.47)	-1.70 (1.72)	-3.03 (2.53)	-1.53 (1.76)			
Month 6	-2.58 (2.18)	-1.63 (1.75)	-2.78 (2.23)	-1.59 (1.89)			
	Percentage of Subjects with $a \ge 50\%$ Reduction						
Month 3	45.9%	23.8%	48.4%	17.6%			
Month 6	34.3%	15.0%	38.7%	17.6%			

TABLE 2. Mean and Standard Deviation of Pain Score Changes fromBaseline and the Percentage of Subjects with at Least a 50% Reduction;Low Dose versus Placebo Group in Phase II Study

The sample size for the primary efficacy endpoints was calculated based on the following assumptions:

- Based on the Phase II findings, it is assumed that the standard deviation of the pain score change from baseline will be 3.0. The true percentage of subjects with a pain reduction of ≥ 50% is assumed to be 35% and 18% for the VM202 group and placebo group, respectively.
- The statistical power is 90% for a detectable mean difference of -1.0 (i.e., mean pain reduction for the VM202 group is higher than that for the Placebo group) for Statistical Hypotheses (I) in Section 4.1 using a t-test. The statistical power is also 90% for Statistical Hypotheses (II) in Section 4.1 provided the assumptions of $p_t = 35\%$ and $p_c = 18\%$ using a chi-square test.
- The two-sided significance level is 0.05. Since a formal statistical conclusion for the second primary efficacy endpoint will not be made unless the null hypothesis of the first primary efficacy endpoint is rejected, no adjustment on the significance level is performed.
- The randomization ratio for the VM202 group and the placebo group is 2:1.

Based on the assumptions above, the sample sizes calculated for the VM202 group and placebo group are 286 and 143 subjects, respectively, for Statistical Hypotheses (I); those for Statistical Hypotheses (II) are 212 VM202 subjects and 106 placebo subjects.

Therefore, 286 VM202 subjects and 143 placebo subjects are needed with data at the 3-month follow-up for the primary data analyses. With a dropout rate of 10%, at least 477 subjects should be randomized in order to have 318 VM202 subjects and 159 placebo subjects.

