6.5 Subgroup Analysis Subsets

The subgroup analyses will be exploratory in nature and will be conducted in the ITT population. The primary and secondary efficacy endpoints will be evaluated based on the categories of the covariates described in Section 4.6 as well as the randomization stratification factor. Age will also be categorized as <65 years and \geq 65 years. These subgroups will be re-examined and may be re-categorized or eliminated due to small sample size (if there are < 10% of subjects within each subgroup) before unblinding for analysis. For example, if < 10% of overall subjects are \geq 65 years, then analyses for this subgroup will not be performed. Descriptive summaries for the primary and secondary efficacy endpoints will also be provided for each study center regardless of the sample size per center, and similarly for the different protocol versions.

Nerve conduction velocity (NCV) analysis will be performed on an NCV sub-population. The NCV sub-population will include all randomized subjects that have at least one postbaseline NCV assessment.

The treatment by subgroup interaction will be examined and tested as described in Section 8.4.5. Data Handling

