8.4.6. Analysis of Covariates

The following covariate analyses will be conducted for the primary and secondary efficacy based on the ITT population to evaluate the treatment effect adjusted for the three covariates listed in Section 4.6:

- The primary analysis model (Section 8.4.2) adding an individual covariate of the three covariates will be used to obtain the 2-sided 95% confidence intervals for the covariate-adjusted estimate of the treatment effect and covariate effect along with their respective p-values.
- The primary analysis model (Section 8.4.2), adding all three covariates will be used to obtain the 2-sided 95% confidence intervals for the covariate-adjusted estimate of the treatment effect.

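### Baseline HbA1c and age enter the exploratory interaction tests and the covariate-adjusted models only as two-group variables; adding continuous terms would be a cheap improvement

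*SAP*

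**What the plan says.** SAP 4.6 describes a secondary examination in which "three additional covariates will be introduced into the model to derive the covariate-adjusted estimates". The three are baseline HbA1c (split at the median), gender, and age (split at 65 years). Three later sections rely on that coding:

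- SAP 6.5 calls the subgroup analyses exploratory and has the primary and secondary endpoints "evaluated based on the categories of the covariates described in Section 4.6". A subgroup variable may be re-categorised or dropped before unblinding if a group holds under 10% of subjects.
- SAP 8.4.5 gives the interaction test: "A subgroup variable will be included in the primary analysis models described in Section 8.4.2 along with its interaction with the treatment effect". At p of 0.05 or more the interaction is called not significant. Below 0.05 the Gail-Simon test follows, as an interpretive aid.
- SAP 8.4.6 aims to "evaluate the treatment effect adjusted for the three covariates listed in Section 4.6", first one covariate at a time and then all three together.

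No analysis of HbA1c or age on its continuous scale appears in either document. Baseline pain, by contrast, is a continuous covariate in the primary model (SAP 8.4.2).

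**The concern.** HbA1c is measured at Screening and Day 0 (protocol 4.2.4), and age at consent is recorded (SAP 8.3). Reducing each to two groups treats a subject just over the cut like one far above it. If the treatment effect drifts steadily with glycaemic control or age, the two-group test is weaker than a test on the measured value. In 8.4.5 the first test also decides whether Gail-Simon is run, so a missed interaction closes off the second step.

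In 8.4.6, a two-group term removes only part of a chance imbalance in HbA1c or age, so an estimate described as adjusted for them is adjusted only in part.

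**Working it through.** **Inputs from SAP 5.** "The two-sided significance level is 0.05"; "The statistical power is 90% for a detectable mean difference of -1.0"; "the standard deviation of the pain score change from baseline will be 3.0"; 286 VM202 and 143 placebo subjects with 3-month data; responder rates of "35% and 18% for the VM202 group and placebo group, respectively".

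**The plan's own figures reproduce.** A two-sample t-test with difference 1.0, SD 3.0 and 2:1 allocation has 90.1% power at 286 + 143. The responder comparison needs 212 + 106 without continuity correction. Dropout: 429 / 0.9 = 476.7, so 477. The documents state no power for any interaction test.

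**Assumptions for the interaction.** Normal modifier, effect changing linearly by d points per SD of the modifier, one visit, share p above the cut. The share aged 65 or over is not given, so I use p = 0.5 (median cut) and p = 0.3 (illustrating the age cut).

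**Step 1, standard error.** 3.0 × √(1/286 + 1/143) = 0.307. This is the SE of the treatment difference and also of the interaction per SD of a continuous modifier.

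**Step 2, information kept by a cut.** φ(z)² / [p(1 − p)], where z is the normal quantile at the cut.

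- p = 0.5: 0.3989² / 0.25 = 0.637
- p = 0.3: 0.3477² / 0.21 = 0.576

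**Step 3, power.** The noncentrality is d / 0.307 for the continuous test. For the cut test it is multiplied by √0.637 = 0.798 or √0.576 = 0.759. Two-sided 5% power:

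| d (points per SD) | Continuous | Cut 50/50 | Cut 30/70 |
|---|---|---|---|
| 0.25 | 13% | 10% | 9% |
| 0.50 | 37% | 25-26% | 23-24% |
| 0.75 | 68% | 50% | 46% |
| 0.86 | 80% | 61% | 57% |
| 1.00 | 90% | 74% | 69% |
| 1.25 | 98% | 90% | 87% |

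Simulation of the single-visit model agrees: at d = 0.86, 79% continuous against 61% at a median cut. Type I error was 0.051 and 0.049, so the cut costs power, not validity.

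**Step 4, the reverse case.** Suppose the effect is a step at the median, with a 1.72-point difference between halves. The SE of the two-group interaction is 2 × 0.307 = 0.615. The categorical test has noncentrality 1.72 / 0.615 = 2.80 and power 80%. The linear test has 2.80 × 0.798 = 2.23 and power 61%. The loss is symmetric.

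**Step 5, sensitivity to the split.** The information lost is 36% at 50/50, 42% at 30/70, 51% at 20/80 and 66% at 10/90, the last being the smallest share SAP 6.5 keeps. Illustrative distributions truncated at the entry limits give 31-33% lost for HbA1c (assumed mean 7.4-7.8, SD 1.2-1.5, maximum 10%) and 44-54% for age (assumed mean 58-62, SD 8-10, maximum 75).

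**Step 6, the adjusted models in 8.4.6.** If a covariate explains a share R² of outcome variance, cutting it inflates the residual variance by (1 − eR²) / (1 − R²), where e is the information kept. Power for a 1.0-point treatment effect:

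- R² = 0.01: 90.5% continuous, 90.4% cut
- R² = 0.10: 92.9% continuous, 92.0% (50/50) or 91.8% (30/70) cut

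The cost is about 0.1 to 1.1 points.

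**The case against.** The strongest reply is that the result depends on a shape the documents do not support. Nothing in them says that modification would be linear rather than a threshold, and Step 4 shows the linear test losing as much in the threshold case. This stands. It rules out replacing the categorical test, but not adding a continuous one beside it.

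Second, the larger losses need large interactions. With an average effect of 1.0 point, d = 0.86 means the effect runs from 1.86 to 0.14 points of benefit across one SD either side of the mean. At d = 1.0 about 16% of subjects would have a reversed effect. At d = 0.25 neither test is informative. This also stands.

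Third, the stakes are low. The subgroup work is exploratory with no planned power, and the adjusted models are a secondary examination. A reader might infer that 8.4.5 issues an all-clear on heterogeneity when p is 0.05 or more. It does not: it says only that the interaction is not significant. The within-subgroup models and descriptive tables for HbA1c and age are produced whatever the p-value.

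Fourth, these powers are for one visit. SAP 8.4.5 uses a three-visit repeated-measures model and a logit model for responders, and power under those was not computed. The powers are therefore illustrative.

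What survives is narrower: the measured values are available, the primary model already carries a continuous baseline term, and the SAP gives no reason for using these two variables only in cut form.

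**Conclusion.** The point holds as a minor improvement. The two-group coding is certain from the text. The size is conditional on a roughly normal modifier, roughly linear modification and a single-visit model at 286/143 with SD 3.0. Under those conditions about 58-64% of the information is kept, and interaction power drops by 11-14 points at d = 0.5 (37% to 24-26%) and by 19-23 points at d = 0.86 (80% to 57-61%). At d = 0.25 the drop is about 3 points, and for a step at the cut the sign reverses.

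A reader might infer a general loss of some 36-42% of the information and a fixed double-digit cost in power. The documents do not support that, because they give neither the distributions of age and HbA1c nor the share aged 65 or over, and Step 5 shows the information loss moving well outside that range. Nor do they support inferring that the main efficacy conclusion is weakened: the primary models use neither variable. In 8.4.6 the gain from continuous terms is fuller adjustment, with negligible gain in power.

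**What to change.** - **SAP 8.4.6 (and 4.6):** enter baseline HbA1c and age as continuous covariates. Gender stays as it is.
- **SAP 8.4.5:** keep the categorical interaction tests. As a supplement, add a treatment-by-continuous-covariate interaction for HbA1c and for age in the same repeated-measures models. State that it is exploratory.
- **Unchanged:** the median and 65-year groups remain for the tables, the within-subgroup models and the Gail-Simon step.

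The cost is a few sentences in the SAP and a small programming change, made before unblinding, with no new data. The downside is one more exploratory test per variable and an assumed linear trend, which the retained categories let readers check. A continuous term also needs no minimum group size, so age could still be examined if the 10% rule in SAP 6.5 removed the age groups.
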